### 5.5.2 Other binary efficacy endpoints

Other binary efficacy endpoints are listed in [Panel 6](#). All binary endpoints take the values '1' (response) or '0' (non-response) depending on whether the condition is met.

The binary efficacy endpoints listed in [Panel 6](#), IGA 0/1 and EASI75 will be tabulated from baseline to Week 16 by visit using the same strategy as for the primary endpoints. Missing values where no intercurrent events have occurred, will be imputed as non-response.

#### Panel 6: Other binary efficacy endpoints

Description of endpoint
EASI90: obtaining at least 90% reduction in EASI score
EASI50: obtaining at least 50% reduction in EASI score
Reduction in Worst Weekly Pruritus NRS/Adolescent's Pruritus NRS of at least 4
Reduction in POEM of at least 4 in adults/ Reduction in POEM of at least 6 in adolescents. Subjects with POEM < 4 for adults / <6 for adolescents at baseline will not be included in the analysis
Reduction in DLQI of at least 4 in adults/Reduction in CDLQI of at least 6 in adolescents. Subjects with DLQI < 4 for adults / CDLQI <6 for adolescents at baseline will not be included in the analysis

### 5.5.3 Other continuous endpoints and patient reported outcomes

The mean, 95% CI and SD will be calculated for the change and percentage change for other continuous efficacy endpoints listed in [Panel 7](#).

THIS DOCUMENT CONTAINS CONFIDENTIAL INFORMATION AND MUST NOT BE COPIED OR MADE AVAILABLE TO ANY THIRD PARTY WITHOUT THE PRIOR WRITTEN CONSENT OF THE LEO PHARMA GROUP

The DLQI will be analysed and presented for adult subjects only, and the CDLQI score will be analysed and presented for adolescent subjects only.

Analysis and data presentation will be based on the FAS.

### Panel 7: Other continuous efficacy endpoints

Description of endpoint
Change in Eczema-related Weekly Sleep NRS will be tabulated from baseline to Week 16 by visit.
Change in Worst Weekly Pruritus NRS/Adolescent's Pruritis NRS will be tabulated from baseline to Week 16 by visit
Change in DLQI/CDLQI will be tabulated from baseline to Week 16 by visit.
Change in POEM will be tabulated from baseline to Week 16 by visit. Percentage change in EASI will be tabulated from baseline to Week 16 by visit.

## 5.6 Pharmacokinetics analysis and antidrug antibodies

### 5.6.1 Pharmacokinetic analysis

All the PK samples in the trial are trough samples. The trough concentration ( $C_{trough}$ ) will be listed and descriptive statistics will be applied.

Missing data will not be imputed.

### 5.6.2 Anti-drug antibodies analysis

Anti-drug antibodies are tabulated as described in the CTP section 14.3.14.

For subjects who develop ADA and are considered treatment boosted or treatment emergent, the IGA score, change in EASI at end of treatment, and titre information will be listed.

Neutralising antibodies (nAb) will be conducted on those serum samples that test positive for ADA. The nAb status will be listed for subjects who develop ADA.

## 5.7 Safety analysis

The analysis of safety will be presented separately for the treatment period and SFU period.

Details on incomplete dates, duplicate measurements, unscheduled visits can be found in the ADRG or Define.xml.

THIS DOCUMENT CONTAINS CONFIDENTIAL INFORMATION AND MUST NOT BE COPIED OR MADE AVAILABLE TO ANY THIRD PARTY WITHOUT THE PRIOR WRITTEN CONSENT OF THE LEO PHARMA GROUP

### 5.7.1 Adverse events

AEs will be coded during the course of the trial according to Medical Dictionary for Regulatory Activities (MedDRA) version 24.0 and presented as described in the CTP section 14.3.12.1.

An AE will be considered treatment emergent if started after the first use of IMP. Only treatment emergent AEs will be summarized and tabulated.

AEs will be presented by preferred terms (PT) and primary system organ class (SOC).

An overall summary of the number (percentage) of AEs, the rate of AEs (number of AEs per 100 patient years of observation time), and the number (percentage) of subjects with any treatment-emergent AEs, death, SAEs, AEs leading to premature discontinuation from IMP and/or withdrawals from the trial, treatment-related AEs, and severe AEs will be presented. In addition, AEs will be presented by severity and causal relationship to IMP.

A summary of all AESIs will be tabulated, and for the AESI injection site reactions, a separate severity grading derived from the data collected according to [Panel 9](#) will be tabulated as described in Section [5.7.2](#)

The number (percentage) of AEs, rate of AEs, and number of subjects with each type of AEs will be tabulated.

SAEs and AESIs will be evaluated separately. A narrative for each SAE will be given.

All AEs recorded during the course of the trial will be included in subject data listings.

### 5.7.2 Adverse events of special interest

The AEs listed in [Panel 8](#) are considered adverse events of special interest (AESIs) in this trial and will have additional details recorded in the eCRF.

#### Injection site reactions

Injection site reactions (ISR)s are considered AEs of special interest (AESIs). Additional information on objective signs and subjective symptoms for ISRs, given in [Panel 9](#), will be provided on the AESI form. The information will be used to derive the severity of each sign/symptom according to the severity grading scale given in [Panel 10](#).

Injection site reactions will be summarised descriptively in terms of number of subjects and percentage of subjects reporting an injection site reaction within each category of the injection site reaction severity grading scale given in [Panel 10](#).

THIS DOCUMENT CONTAINS CONFIDENTIAL INFORMATION AND MUST NOT BE COPIED OR MADE AVAILABLE TO ANY THIRD PARTY WITHOUT THE PRIOR WRITTEN CONSENT OF THE LEO PHARMA GROUP

Furthermore, all ISRs will be listed in the subject data listings.

### Panel 8: Adverse events of special interest

Adverse event of special interest	Additional data to be included in the eCRF (if available)
Injection site reactions	See Panel 9 for details.
Eczema herpeticum	
Skin findings:
 
 
• Lesion type (papules, vesicles, crusts, eroded pits, other).
 
• Disseminated/localised.
 
• Location (face, scalp, back, chest, upper limb, lower limb, genitals).
 
• Present in an area with visible eczema / no visible eczema / present in areas with and without eczema.
 
• Monomorphic/polymorphic.
 
 
Confirmation of herpes simplex virus (not confirmed, PCR, viral culture, Tzanck, other).

Malignancy diagnosed after treatment assignment, excluding basal cell carcinoma, localised squamous cell carcinoma of the skin, and carcinoma in situ of the cervix	
 
• Histology report available.
 
• Oncology assessment available.
 
• Treatments (surgery, radiation, chemotherapy, other).
 

Skin infection requiring systemic treatment	
 
• Location (face, scalp, back, chest, upper limb, lower limb, genitals).
 
• Outcome of pathogenic swab (positive, negative, not performed).
 

Conjunctivitis	
 
• Aetiology (viral, bacterial, allergic, unknown).
 
• Bacterial culture outcome (for events with bacterial aetiology).
 
• Diagnosis confirmed by ophthalmologist.
 

Keratoconjunctivitis	
 
• Aetiology (infectious, non-infectious, other, unknown).
 
• Bacterial culture outcome (for events with bacterial aetiology).
 
• Diagnosis confirmed by ophthalmologist.
 

Keratitis	
 
• Aetiology (infectious, non-infectious, other, unknown).
 
• Bacterial culture outcome (for events with bacterial aetiology).
 
• Diagnosis of herpes simplex keratitis (for events with viral aetiology).
 
• Diagnosis confirmed by ophthalmologist.
 

**Abbreviations:** eCRF = electronic case report form, PCR=polymerase chain reaction

THIS DOCUMENT CONTAINS CONFIDENTIAL INFORMATION AND MUST NOT BE COPIED OR MADE AVAILABLE TO ANY THIRD PARTY WITHOUT THE PRIOR WRITTEN CONSENT OF THE LEO PHARMA GROUP

### Panel 9: Adverse events of special interest - injection site reaction

Adverse event of special interest	Additional data to be collected	
Injection site reactions	Objective signs	
Erythema
 
 
• Largest diameter (mm)
 
 
Swelling/Oedema
 
 
• Largest diameter (mm)
 
• Effect on activity 
 
○ Does not interfere with activity
 
○ Interferes with activity
 
○ Prevents daily activity
 
 
 
 
Bruising/Haematoma
 
 
• Largest diameter (mm)
 
• Effect on activity 
 
○ Does not interfere with activity
 
○ Interferes with activity
 
○ Prevents daily activity
 
 
 
 
Induration
 
 
• Largest diameter (mm)
 
• Effect on activity 
 
○ Does not interfere with activity
 
○ Interferes with activity
 
○ Prevents daily activity
 
 
 
 
Other
 
 
• Description
 
• Largest diameter (mm)
 
• Effect on activity 
 
○ Does not interfere with activity
 
○ Interferes with activity
 
○ Prevents daily activity
 
 
 

	Subjective symptoms	
Itch
 
 
• Effect on activity 
 
○ Does not interfere with activity
 
○ Interferes with activity
 
○ Prevents daily activity
 
 
 
 
Pain/Burning/Stinging
 
 
• Effect on activity 
 
○ Does not interfere with activity
 
○ Interferes with activity
 
○ Prevents daily activity
 
 
 
 
Other
 
 
• Description
 
• Effect on activity 
 
○ Does not interfere with activity
 
○ Interferes with activity
 
○ Prevents daily activity
 
 
 

THIS DOCUMENT CONTAINS CONFIDENTIAL INFORMATION AND MUST NOT BE COPIED OR MADE AVAILABLE TO ANY THIRD PARTY WITHOUT THE PRIOR WRITTEN CONSENT OF THE LEO PHARMA GROUP

### Panel 10: Injection site reaction severity grading scale

Injection site reaction	Mild (Grade 1)	Moderate (Grade 2)	Severe (Grade 3)
Pain	Does not interfere with activity	Interferes with activity	Prevents daily activity
Itching	Does not interfere with activity	Interferes with activity	Prevents daily activity
Erythema	2.5 to 5 cm	5.1 to 10 cm	> 10 cm
Swelling/Oedema	2.5 to 5 cm and does not interfere with activity	5.1 to 10 cm or interferes with activity	> 10 cm or prevents daily activity
Bruising/Hematoma	2.5 to 5 cm and does not interfere with activity	5.1 to 10 cm or interferes with activity	> 10 cm or prevents daily activity
Induration	2.5 to 5 cm and does not interfere with activity	5.1 to 10 cm or interferes with activity	> 10 cm or prevents daily activity

Symptoms assessed and found not present will be graded 0.

#### 5.7.3 Vital signs

Vital signs, observed values and change from baseline, will be summarised at each site visit using mean, standard deviation (SD), median, 1st quartile, 3rd quartile, minimum, and maximum values.

#### 5.7.4 Clinical laboratory evaluation

Laboratory parameters (chemistry and haematology) – observed values and change from baseline – will be summarised at each site visit using mean, SD, median, 1st quartile, 3rd quartile, minimum, and maximum values.

Urinalysis dipstick results and urinalysis investigator interpretation will be listed.

Laboratory parameters (chemistry and haematology), except eosinophils, will be classified as ‘low’, ‘normal’, or ‘high’, depending on whether the value is below, within, or above the reference range, respectively. Eosinophils will be classified at ‘≤ 0.5’, ‘>0.5 and ≤1.5’, or ‘>1.5’. Three shift tables will be produced; one showing the categories at baseline against those at end of treatment (Week 16), one showing the categories at baseline against the highest post-baseline value, and one showing the categories at baseline against the lowest post-baseline value.

THIS DOCUMENT CONTAINS CONFIDENTIAL INFORMATION AND MUST NOT BE COPIED OR MADE AVAILABLE TO ANY THIRD PARTY WITHOUT THE PRIOR WRITTEN CONSENT OF THE LEO PHARMA GROUP

Mean plots with standard deviation (SD) by visit and boxplots of actual values will be presented for the selected laboratory parameters listed below:

- chemistry (alkaline phosphatase, alanine aminotransferase, aspartate aminotransferase, total bilirubin, gamma glutamyl transferase)
- haematology (basophils, eosinophils, leukocytes, lymphocytes, monocytes, neutrophils)

Furthermore, the mean plots with SD by visit will be presented for the change from baseline for the aforementioned selected chemistry and haematology parameters.

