23. History of attempted suicide or at significant risk of suicide (either in the opinion of the investigator or defined as a "yes" to suicidal ideation questions no. 4 or 5 or answering "yes" to suicidal behaviour on the Columbia-Suicide Severity Rating Scale [C-SSRS] screening version).

24. Any disorder, including but not limited to, cardiovascular, gastrointestinal, hepatic, renal, neurological, musculoskeletal, infectious, endocrine, metabolic, haematological, immunological, psychiatric, or major physical impairment that is not stable, in the opinion of the investigator, and could:

- Affect the safety of the subject throughout the trial.
- Influence the findings of the trial or their interpretations.
- Impede the subject's ability to complete the entire duration of trial.

25. Any clinically significant abnormal findings in physical examination, vital signs, haematology, clinical chemistry, or urinalysis during the screening period, which in the opinion of the investigator, may put the subject at risk because of his/her participation in the trial, or may influence the results of the trial, or the subject's ability to complete entire duration of the trial.

26. Alanine aminotransferase (ALT) or aspartate aminotransferase (AST) level ≥ 2.0 times the upper limit of normal (ULN) at screening.

27. Positive hepatitis B surface antigen (HBsAg), hepatitis B surface antibody (HBsAb), hepatitis B core antibody (HBcAb) at screening. Subjects with positive HBsAb are eligible in the trial provided they have negative HBsAg and HBcAb.

28. Positive hepatitis C virus antibody (anti-HCV) serology at screening.

THIS DOCUMENT CONTAINS CONFIDENTIAL INFORMATION AND MUST NOT BE COPIED OR MADE AVAILABLE TO ANY THIRD PARTY WITHOUT THE PRIOR WRITTEN CONSENT OF THE LEO PHARMA GROUP

29. Subjects who are not willing to abstain from donating blood and/or plasma from the time of informed consent and for 16 weeks (5 half-lives) after last dose of IMP.
30. Subjects who are legally institutionalised.
31. Pregnant, breastfeeding, or lactating women.
32. Employees of the trial site or any other individuals directly involved with the planning or conduct of the trial, or immediate family members of such individuals.

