10.2 Reasons for discontinuation of IMP

10.2.1 Reasons for permanent discontinuation of IMP

Subjects will permanently discontinue IMP in the event of:

- Anaphylactic reaction or other severe systemic reaction to IMP injection.
- An AE that, in the opinion of the investigator or sponsor's medical expert, contraindicates further dosing.
- Diagnosis of a malignancy during the trial, excluding carcinoma in situ of the cervix, or localised squamous or basal cell carcinoma of the skin.
- Evidence of pregnancy (e.g. a positive pregnancy test).
- Any infection that is opportunistic, such as active tuberculosis and other infections whose nature or course may suggest an immuno-compromised status.
- Severe laboratory abnormalities:
 - Alanine aminotransferase (ALT) or aspartate aminotransferase (AST) values $>3\times\text{ULN}$ with total bilirubin $>2\times\text{ULN}$ (unless elevated bilirubin is related to Gilbert-Meulengracht Syndrome).
 - Confirmed AST or ALT $>5\times\text{ULN}$ for >2 weeks.

THIS DOCUMENT CONTAINS CONFIDENTIAL INFORMATION AND MUST NOT BE COPIED OR MADE AVAILABLE TO ANY THIRD PARTY WITHOUT THE PRIOR WRITTEN CONSENT OF THE LEO PHARMA GROUP

Data to be recorded in the eCRF

The primary reason for permanent discontinuation of IMP must be recorded in the medical records and on the end-of-treatment form in the eCRF where the following options are available:

- Adverse event (a specification must be provided).
- Death.
- Lost to follow-up.
- Withdrawal by subject.
- Withdrawal by parent/guardian (applicable for adolescent subjects).
- Lack of efficacy.
- Pregnancy.
- Other (a specification must be provided).

It will also be recorded whether the discontinuation of IMP was related to the COVID-19 pandemic.

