11.5.3.2 Investigator evaluation of laboratory samples

Central laboratory

Chemistry, haematology, serology, pregnancy tests (serum), and urinalysis (if applicable) will be analysed by a central laboratory which will provide results to the trial sites. The investigator must evaluate all results outside the reference range ('clinically significant' or 'not clinically significant') and sign and date the evaluation. The signed and dated version will be filed with the investigator's trial documentation. In case of clinically significant abnormal results, appropriate action, as judged by the investigator, must be taken.

In case of an increase of alanine aminotransferase (ALT) or aspartate aminotransferase (AST) $\geq 5 \times \text{ULN}$ re-sampling for alkaline phosphatase (ALP), ALT, AST, and bilirubin (BILI) should be done immediately, without undue delay and no later than within 72 hours from initial sampling time to confirm abnormalities. Re-sampling may be relevant at lower levels at the discretion of the investigator. In case of re-sampling, analysis should be done at central laboratory.

Abnormal liver function tests of concurrent measurements of alanine aminotransferase (ALT) or aspartate aminotransferase (AST) $\geq 3 \times \text{ULN}$ and bilirubin (BILI) $\geq 2 \times \text{ULN}$ should be reported as an SAE (see Section 13.4 for reporting of SAEs).

If a screening laboratory result is abnormal and clinically significant, it will be at the investigator's discretion to decide if the subject should be included in the trial.

A laboratory manual will be provided to the trial sites specifying the procedures for collection, processing, storage, and shipment of samples, as well as laboratory contact information specific to this trial.

Tests performed at the trial site

Urine samples will be tested with a dipstick according to the schedule of trial procedures (Section 4). It will be at the investigators discretion to decide whether a urine sample should be sent to the central laboratory for further analysis.

Women of childbearing potential will have a urine pregnancy test performed at the trial site as shown in the schedule of trial procedures in Section 4.

Reporting in eCRF

It will be recorded in the eCRF if a blood sample was taken. If not, a reason should be provided. The investigator's assessment of the results ('normal', 'abnormal, not clinically

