THIS DOCUMENT CONTAINS CONFIDENTIAL INFORMATION AND MUST NOT BE COPIED OR MADE AVAILABLE TO ANY THIRD PARTY WITHOUT THE PRIOR WRITTEN CONSENT OF THE LEO PHARMA GROUP

significant', 'abnormal, clinically significant') will be recorded in the eCRF.

Site staff will record in the eCRF if a urine dipstick was performed and whether urinalysis is required for further assessment, as judged by the investigator. If so, a urine sample should be sent to the central laboratory. If the urine sample was not tested with a dipstick, a reason will be provided. In case urinalysis is performed, the investigator's assessment of the results ('normal', 'abnormal, not clinically significant', 'abnormal, clinically significant') will be recorded in the eCRF.

It will be recorded in the eCRF if the subject is a woman of childbearing potential and if a urine pregnancy test was performed. If not, a reason should be provided. Also, the date and the outcome of the urine pregnancy test will be recorded in the eCRF ('positive', 'negative').

Clinically significant abnormal laboratory results at the screening visit will be documented as medical history in the eCRF. At subsequent visits, any clinically significant deterioration of a pre-existing condition will be reported as an AE. Any new clinically significant sign, symptom, or illness occurring after screening will be reported as an AE in accordance with Section 13.3.

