Appendix 1: Definitions of adverse events and serious adverse events

Adverse event definition

An AE is defined as any untoward medical occurrence in a patient or clinical investigation subject administered a pharmaceutical product and which does not necessarily have a causal relationship with this treatment. An AE can therefore be any unfavourable and unintended sign (including an abnormal laboratory finding), symptom, or disease temporally associated with the use of a medicinal (investigational) product, whether or not related to the medicinal (investigational) product (38).

This definition includes:

- Accidental injuries.
- Events related to trial procedures.
- Reasons for any unfavourable and unplanned change in medication (drug and/or dose).
- Clinically significant worsening of pre-existing conditions.
- Reasons for admission to hospital or surgical procedures*.
- AEs commonly observed and AEs anticipated based on the pharmacological effect of the IMP.
- Any laboratory abnormality assessed as clinically significant by the investigator (see Section 11.5.3.2).

Serious adverse event definition

An SAE is any untoward medical occurrence that:

- Results in death.
- Is life-threatening – at risk of death at the time of the SAE (not an event that hypothetically might have caused death if more severe).
- Requires in-patient hospitalisation or prolongation of existing hospitalisation*.
- Results in persistent or significant disability or incapacity.
- Is a congenital anomaly or birth defect.

THIS DOCUMENT CONTAINS CONFIDENTIAL INFORMATION AND MUST NOT BE COPIED OR MADE AVAILABLE TO ANY THIRD PARTY WITHOUT THE PRIOR WRITTEN CONSENT OF THE LEO PHARMA GROUP

- Is a medically important condition. Events that may not be immediately life-threatening or result in death or hospitalisation but may jeopardise the subject or may require intervention to prevent one of the other outcomes listed in the definition above. Examples are intensive treatment in an emergency room or at home for allergic bronchospasm, blood dyscrasias, and convulsions that do not result in hospitalisation, development of drug dependency, or drug abuse.

Additionally, all malignancies, including skin malignancies, should be reported as SAEs.

*Hospitalisation for procedures or treatments planned prior to the subject consented to trial participation do not constitute an AE and should therefore not be reported as AE or SAE.

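### Liver tests are tabulated only as low, normal or high, so no planned table counts subjects reaching the protocol's liver action levels independently of investigator judgement (mainly isolated ALT/AST ≥5×ULN)

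*SAP*

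**What the plan says.** **Tabulation.** In SAP 5.7.4, "Laboratory parameters (chemistry and haematology), except eosinophils, will be classified as" low, normal or high by the reference range. Three shift tables set the baseline category against Week 16, against the highest post-baseline value and against the lowest. One parameter has its own steps: "Eosinophils will be classified at" ≤0.5, >0.5 to ≤1.5, or >1.5. ALT, AST and bilirubin are chemistry parameters (Protocol Panel 8) and have none. Protocol 14.3.12.3 plans reference-range categories too, and SAP Panel 11 adds no table by ULN multiple.

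**Action levels.** The protocol uses ULN multiples when a site must act:
- Protocol 11.5.3.2: at ALT or AST ≥5×ULN, a repeat sample is due "no later than within 72 hours from initial sampling time to confirm abnormalities".
- Protocol 11.5.3.2: concurrent ALT or AST ≥3×ULN and bilirubin ≥2×ULN is an SAE.
- Protocol 10.2.1, under "Severe laboratory abnormalities": treatment stops permanently at ALT or AST >3×ULN with total bilirubin >2×ULN (Gilbert-Meulengracht syndrome excepted), or at a confirmed >5×ULN lasting more than 2 weeks.

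**Baseline.** Exclusion criterion 26 removes "Alanine aminotransferase (ALT) or aspartate aminotransferase (AST) level ≥ 2.0 times the upper limit of normal (ULN) at screening", so a subject can enter between 1× and 2×ULN. SAP 5.1.1 takes the latest pre-dose assessment as baseline.

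**Other outputs.** SAP 5.7.4 gives by-visit summaries of values and changes, including maxima, and boxplots of actual values that cover the liver tests. Protocol 14.3.12.3 adds a listing of subjects outside the reference range. Each SAE gets a narrative (Protocol 14.3.12.1, SAP 5.7.1). An isolated abnormal result becomes an AE under Appendix 1 of the protocol if it is "Any laboratory abnormality assessed as clinically significant by the investigator".

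**The concern.** The categories do not fit the levels that matter in this trial. Once a value passes ULN the table has no further step, so a trivial excursion and one that triggers urgent re-sampling look the same. A subject who starts slightly above ULN and then rises several-fold reads as high at both times. Nothing in the separate tables shows whether raised ALT and raised bilirubin belong to one subject.

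Safety is the trial's secondary objective, and the SAP plans an adults-only interim report to support a marketing submission. A reader of that report will want to know how many subjects reached 5×ULN. The planned AE tables answer only for results that an investigator judged clinically significant. The trial is open-label, so cut-offs are better fixed beforehand than chosen once values have been seen.

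**Working it through.** There is no stated figure to reproduce. The check applies the SAP rule to example values, then asks which planned output would give a count at each action level.

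**1. The shift table (baseline against highest value).** Values are in multiples of ULN; above 1× is high. The values are illustrative. The 1.9× baseline is consistent with exclusion criterion 26.

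| Baseline | Highest post-baseline | Cell | Reaches ≥5×? |
|---|---|---|---|
| 0.8 | 1.05 | normal to high | no |
| 0.8 | 3 | normal to high | no |
| 0.8 | 5 | normal to high | yes |
| 0.8 | 10 | normal to high | yes |
| 1.9 | 1.2 | high to high | no |
| 1.9 | 1.9 | high to high | no |
| 1.9 | 5 | high to high | yes |
| 1.9 | 10 | high to high | yes |

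Eight different courses fall into two cells. In the second, a fall, no change and a five-fold rise (10/1.9 = 5.3) cannot be told apart.

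**2. Concurrency.** Take two subjects with (ALT, bilirubin) in multiples of ULN:
- Pair A: (3.5, 2.5) and (0.8, 0.8). One high ALT, one high bilirubin; one subject meets ≥3× with ≥2×.
- Pair B: (3.5, 0.8) and (0.8, 2.5). One high ALT, one high bilirubin; none meets it.

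The separate tables are identical, but the concurrent count is 1 or 0.

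**3. By-visit maxima.** Treatment-period chemistry is taken at Weeks 4, 12 and 16 (Protocol Panel 2). Suppose the maximum ALT is ≥5×ULN at all three visits. That fits one subject seen three times, three different subjects, or more. With the planned n = 130 and the Wilson interval that SAP 5.1 uses for binary endpoints,

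(p + z²/2n ± z√(p(1−p)/n + z²/4n²)) / (1 + z²/n), with z = 1.96:

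- 1/130 = 0.8%: (0.02247 ± 0.02107)/1.02955, or 0.14% to 4.23%.
- 3/130 = 2.3%: (0.03785 ± 0.02974)/1.02955, or 0.79% to 6.57%.

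These counts are hypothetical. They show only that a maximum does not fix the number of subjects. Conversely, if every by-visit maximum is below 5×ULN, the count at scheduled visits is already known to be zero.

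**4. What each level already has.**

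| Level | Consequence | Planned output | Count free of investigator judgement? |
|---|---|---|---|
| ALT/AST ≥3× with bilirubin ≥2× | SAE | SAE tables and a narrative | No, but the case is covered if the site reports it |
| >3× with >2×, or confirmed >5× for >2 weeks | permanent discontinuation | discontinuation reasons; AEs leading to discontinuation | No, but the case is covered; the reason is recorded as an AE or other, with a specification |
| Isolated ALT/AST ≥5×, no stopping rule met | re-sampling | listing, maxima, boxplots; AE tables only if judged clinically significant | No |

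The last row is the main gap.

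**The case against.** The strongest reply is that nothing in the documents is broken. Protocol 14.3.12.3 asks for reference-range categories and one shift table. The SAP delivers both and adds two worst-value tables, giving alignment with earlier tralokinumab trials as its reason. The ULN multiples are instructions for sites, and no text says they must also be table categories. Special steps for eosinophils do not oblige the SAP to grade other tests. The secondary endpoints are treatment-emergent AEs and ADA, no hepatic event is among the AESIs, and the protocol reports no safety concern in 4,465 exposed subjects. The laboratory data are central and electronic, so a count by ULN multiple is a simple filter that could be run at any time.

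Most of this stands. It shows that the plan is consistent with the protocol and keeps the point small. It does not supply the count. The same ease of filtering is also a reason to specify the table now.

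A reader might go further and infer that serious liver cases could go unseen. The documents do not support that. The combined level is an SAE with a narrative. The out-of-range listing still applies, since the SAP supplements the protocol and Panel 11 does not withdraw it. The maxima of values and changes would show an extreme result. Nor should one infer that re-samples are lost: SAP 5.7 leaves unscheduled visits to the ADRG or Define.xml, and no gap is claimed there.

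**Conclusion.** The point holds as one about tabulation and is minor: a cheap improvement. SAP 5.7.4 places every ALT, AST and bilirubin value above ULN in a single category. As a result, no planned table gives an investigator-independent count of subjects at the protocol's liver action levels. The practical gap is isolated ALT/AST ≥5×ULN that meets no stopping rule. For the combined level, a count derived from the data would only cross-check SAE reporting that is already in place.

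The conclusion rests on the text of the two documents. The example values in the working are illustrative, and no rate of liver abnormality is assumed. The sample size and the primary analysis are unaffected. Finer categories would not make up for the absent control group; they would only state plainly how many subjects reached each level.

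**What to change.** Keep the three shift tables. Add to SAP 5.7.4:

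1. One table of baseline against highest post-baseline value in ULN multiples.
   - ALT and AST: ≤1×, >1 to <3×, 3 to <5×, ≥5×.
   - Total bilirubin: ≤1×, >1 to <2×, ≥2×.
2. One count of subjects with concurrent ALT or AST ≥3×ULN and bilirubin ≥2×ULN, labelled as a cross-check on SAE reporting.

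Present both for all subjects, adults and adolescents, as Protocol 14.3 requires for all results, and record them in Panel 11.

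The cut-offs follow the ≥ limits in Protocol 11.5.3.2. They do not reproduce the stopping rules in 10.2.1, which use strict inequalities and a duration and can stay with discontinuation reporting. The isolated 3×ULN cut for ALT/AST and the isolated 2×ULN cut for bilirubin are descriptive only.

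The cost is one extra table and one count that may have no counterpart in earlier tralokinumab outputs. Visits, samples and site rules do not change.
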